5.2.3 Secondary Endpoints

Data supporting the following endpoints will be collected for both the CEAP 2-5 Randomized Studies as well as the VLU Study. When appropriate, data will be evaluated for the CEAP 2-5 Randomized Studies to compare the VenaSeal™ system to surgical stripping or ETA. Data may also be pooled for all VenaSeal™ system subjects from the CEAP 2-5 Randomized Studies and VLU Study as appropriate. The surgical stripping data will be collected up to the 12 months' time point.

Effectiveness secondary endpoints

1. Anatomic closure of primary target vein at 30 days, and 12, 24, 36, 48 and 60 months:
 - For subjects treated with the VenaSeal™ system or ETA it is defined as DUS showing vein closure along the entire treated vein segment with no discrete segments of patency exceeding 5 cm.
 - For subjects treated with surgical stripping this is defined as absence of refluxing or residual vein and it will be collected at 30 days and 12 months only.
2. Anatomic closure of target vein at 30 days, and 6, 12, 24, 36, 48 and 60 months:
 - For subjects treated with the VenaSeal™ system or ETA this is defined as DUS showing vein closure along the entire treated vein segment with no discrete segments of patency exceeding 5 cm.
 - For subjects treated with surgical stripping this is defined as absence of refluxing or residual vein and it will be collected at 30 days, 6 and 12 months only.
3. Technical success of each target vein immediately post-index procedure:
 - For subjects treated with the VenaSeal™ system or ETA this is defined as DUS showing vein closure along the entire treated vein segment with no discrete segments of patency exceeding 5 cm.
 - For subjects treated with surgical stripping this is defined as absence of refluxing or residual vein.
4. Reintervention of any target vein (including primary target vein) through 60 months, assessed at each follow-up visit (through 12 months for subjects enrolled in the VenaSeal vs. Surgical Stripping Study).
5. Time to reintervention of any target vein (including primary target vein) through 60 months, as measured by the time between the index procedure and the first reintervention procedure (through 12 months for subjects enrolled in the VenaSeal vs. Surgical Stripping Study).

Safety secondary endpoints

6. Adverse events (AEs) occurring in the target limb, evaluated from index procedure through 12 months:
 - Hypersensitivity to VenaSeal™ adhesive
 - Phlebitis
 - Granuloma

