 - Endovenous glue induced thrombosis (EGIT) or endovenous heat induced thrombosis (EHIT)
 - Symptomatic deep vein thrombosis (DVT) events
7. Additional events evaluated through 60 months (through 12 months for subjects enrolled in the VenaSeal vs. Surgical Stripping Study):
 - Symptomatic pulmonary embolism (PE)
 - Serious adverse events (SAEs)

Healthcare utilization secondary endpoints

8. Number and type of adjunctive treatments conducted through 12 months post-index procedure.
9. Healthcare utilization related to the target limb VRD, as determined by the number of healthcare visits conducted, and other health-related resources utilized (e.g., home healthcare services) between study visits through 60 months (30 days, 6 and 12 months only for subjects enrolled within the VenaSeal vs. Surgical Stripping Study).
10. Procedures, tests and treatment of AEs related to the treatment modality or index procedure.
11. VLU Study: Healthcare utilization and routine wound care treatments between study visits through 60 months.

Patient Experience secondary endpoints

12. Time to return to normal activities as reported by the patients.
13. Intra-procedural and post-procedural pain at the index procedure, and 7 days and 30 days as reported by the patient using the numeric rating scale (NRS) with a scale of 0-10.
14. Change in venous disease symptoms at 7 and 30 days, and at 6, 12, 24, 36, 48, and 60 months compared to baseline (7 days, 30 days, 6 and 12 months only for subjects enrolled in the VenaSeal vs. Surgical Stripping Study), as measured by the revised Venous Clinical Severity Score (rVCSS) and subject self-reporting.

15. Change in AVVQ score at 30 days, and 6, 12, 24, 36, 48, and 60 months (30 days, 6 and 12 months only for subjects enrolled in the VenaSeal vs. Surgical Stripping Study) compared to baseline.
16. Change in EuroQoL Group 5-Dimension Self-Report Questionnaire (EQ-5D-5L) at 30 days, and 6, 12, 24, 36, 48 and 60 months (30 days, 6 and 12 months only for subjects enrolled in the VenaSeal vs. Surgical Stripping Study) compared to baseline.
17. Change in the 36-Item Short Form Health Survey (SF-36) reported by the patient at 30 days, and 6 and 12 months compared to baseline.
18. Change in the Venous Dependent Quality of Life (VenousDQoL) reported by the patient at 30 days, and 6, 12, 24, 36, 48, and 60 months (30 days, 6 and 12 months only for subjects enrolled in the VenaSeal vs. Surgical Stripping Study) compared to baseline.

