Post-index procedure, DUS evaluation is required to assess target vein (including primary target vein) closure after VenaSeal™ system or ETA treatment and absence of refluxing vein or residual vein after surgical stripping. DUS is also used for thrombus assessment. This DUS assessment will also be performed at 7 days, 30 days, 6, 12, 24, 36, 48 and 60 months. This DUS assessment could be completed on the day of the follow-up visit or anytime during the follow-up visit window, as applicable to the site's standard scheduling process.

Patient-Reported Symptoms

Subjects will be asked to report symptoms related to their target limb: pain, aching, itching, burning, sensitivity, heaviness and swelling, and asked to identify their dominant symptom from this list. This will be assessed at baseline and at follow-up visits through 12 months. These questions must be completed by the subject and a translation will be available in each of the applicable languages; however, designated site staff may verbally read the symptom list to the patient.

Venous Treatment Satisfaction Questionnaire (VenousTSQ)

The two components of the VenousTSQ are evaluated as two separate primary endpoints in this study. The questionnaire needs to be completed either by the subject or by a delegated person who asks the questions to the subject and completes the questionnaire on behalf of the subject. This should be the first subject-reported assessment at all study visits when administered.

The Venous Treatment Satisfaction Questionnaire (VenousTSQ) is a new Patient Reported Outcome Measure (PROM). Via a qualitative design approach involving patient interviews and clinical expert reviews, the process resulted in an independently developed tool for venous patients. The tool consists of two components, the peri-procedural early component of treatment satisfaction which will be measured at 30 days post index-procedure (VenousTSQe), and the longer-term status component of treatment satisfaction which can be measured at 30 days, 6 and 12 months (VenousTSQs). Questions focus on topics relevant for patients with varicose veins who have undergone a venous treatment and include items on treatment satisfaction/dissatisfaction, symptoms such as pain, and outcome satisfaction/dissatisfaction.

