12.3. Recording and Reporting of Adverse Events

Events will be recorded on the appropriate CRFs entering information as documented in the subject's medical records. Events will be reported throughout the course of study (from the moment the index procedure is initiated until completion of follow up or exit). Due to the post market nature of this study, only adverse events meeting the below criteria will be reported).

1. All AEs occurring in the target limb, including but not limited to the following specific events:
 - Hypersensitivity
 - Phlebitis
 - Granuloma
 - Endovenous glue induced thrombosis (EGIT) or endovenous heat induced thrombosis (EHIT)
 - Symptomatic DVT.
2. Symptomatic PEs
3. Serious adverse events (SAE)
4. Non-subject (users) adverse events: AEs occurring to the users or other site personnel related to the device or the procedure.

For all reportable AEs, investigators should assess and record at least the following information on the AE CRF:

1. Date the event started (if full date is not available, partial date is allowed)
2. Date site became aware of event
3. Date event first determined to be a Serious Adverse Event, if applicable
4. Event term
5. Event description
6. Action taken/treatment
7. Which seriousness criteria did the event meet, if applicable
8. Relationship of the event to the procedure
9. Relationship of the event to the device (for VenaSeal™ and ETA treatment only)
10. Narrative (describe any additional details relevant to the AE)
11. Outcome of the event.

Events described in **Table 13** are considered unavoidable events inherent to surgical procedure that is expected to occur in all subjects for a projected duration according to the Investigator's opinion. Unavoidable events should not be reported unless the event worsens or is present outside the stated timeframe from the index procedure.

Table 13: Expected and Unavoidable not to be reported adverse events

Event Description	Timeframe from the procedure
Anesthesia related nausea/vomiting	24 hours
Low-grade fever (<100°F or <37.8°C)	48 hours
Incisional pain (with or without standard treatment and patient not returning to clinic to have additional treatment)	72 hours
Mild to moderate bruising / ecchymosis *	7 days
Back pain related to laying on table	72 hours

Bleeding at access site (not requiring treatment)	24 hours
Emergency room visits and procedures not meeting the SAE definition**	NA

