7.9.1.5 Safety secondary endpoints

1. Adverse events (AEs) occurring in the target limb, evaluated from index procedure through 12 months.

Hypothesis

There is no formal hypothesis test for this study objective.

Endpoint Definition

Adverse events occurring in the target limb defined as any of the following:

- Hypersensitivity to VenaSeal™ adhesive, defined as an allergic reaction to the VenaSeal™ adhesive. The presence of hypersensitivity is confirmed through adjudication. Relatedness to a study procedure and relatedness to the study device are defined.
- Phlebitis, defined as inflammatory reaction of a treated vein. The presence of phlebitis is confirmed through adjudication. Relatedness to a study procedure and relatedness to the study device are defined.
- Granuloma, defined as a grouping of macrophages. The presence of granuloma is confirmed through adjudication. Relatedness to a study procedure and relatedness to the study device are defined.
- Endovenous glue induced thrombosis (EGIT) or endovenous heat induced thrombosis (EHIT) for VenaSeal or Thermal Ablation, defined as extensions of a thrombus that extend from the treated vein into the deep venous system. The presence of a glue extension, thrombus extension, or combination glue/thrombus is confirmed through DUS visualization of the extension into the common femoral vein or popliteal vein from the target vein and extension length is specified.

CEC determination of the above events will be used for reporting.

Analysis Methods

Adverse events that are in any of the above enumerated categories will be characterized. Adverse events will be categorized per the specified definitions, and then summarized by study group.

Determination of Subjects for Analysis

The safety analysis will consist of the ITT population.

2. Additional events evaluated through 12 months:

- Symptomatic deep vein thrombosis (DVT) events

- Symptomatic Pulmonary embolism (PE)
- Serious adverse events (SAEs)

Hypothesis

There is no formal hypothesis test for this study objective.

Endpoint Definition

CEC determination of serious adverse events will be used for reporting. The MedDRA codes for Deep vein thrombosis and Pulmonary embolism will be used for reporting of DVT and PE adverse events.

Analysis Methods

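### The SAP counts symptomatic DVT by MedDRA code alone, without the symptom and target-limb conditions that protocol endpoint 6 sets

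*SAP*

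**What the plan says.** Protocol 5.2.3, safety endpoint 6, is headed "Adverse events (AEs) occurring in the target limb, evaluated from index procedure through 12 months", and its last item is "Symptomatic deep vein thrombosis (DVT) events". That sets three conditions: symptoms, target limb and 12 months. Symptomatic PE belongs to endpoint 7, which has no limb condition.

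SAP 7.9.1.5 splits this differently. Item 1 (target-limb AEs) contains hypersensitivity, phlebitis, granuloma and EGIT/EHIT. Each has a definition and is reported by CEC determination. DVT is not in that list. It appears in item 2 with PE and SAEs, still labelled symptomatic, and the only operative text is "The MedDRA codes for Deep vein thrombosis and Pulmonary embolism will be used for reporting of DVT and PE adverse events". Events and patients are then counted by arm, with no hypothesis test. SAP 7.9.2.4 (item 2) uses the same sentence for the VLU Study, under a 60-month heading.

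On collection, Protocol 12.3 makes reportable "All AEs occurring in the target limb, including but not limited to the following specific events", with symptomatic DVT as one of the named examples. For PE it is narrower: "Symptomatic PEs". On imaging, Protocol 10.5 says "DUS is also used for thrombus assessment" and "This DUS assessment will also be performed at 7 days, 30 days, 6, 12, 24, 36, 48 and 60 months".

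**The concern.** The code, as the SAP names it, identifies a diagnosis. It does not say whether the patient had symptoms or which limb was involved. If it is the whole counting rule, the row headed symptomatic DVT holds every event coded as deep vein thrombosis, and its content differs from the protocol endpoint of the same name.

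DVT is the only component of endpoint 6 left with neither a definition nor CEC determination in the SAP. Few true events are likely: of the studies in Protocol 4.1, WAVES reported no DVT in 50 subjects, and VeClose reported one among 222 randomized subjects, in the non-index limb. With counts that small, one or two events that do not belong can dominate the row. The trial is open-label (Protocol 6), so settling doubtful cases at the reporting stage would mean deciding them with the arm known.

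**Working it through.** The documents state no DVT rate, so there is no plan figure to reproduce. The check sets the texts side by side and then asks whether anything upstream restores the missing conditions.

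**1. Conditions in each place**

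| Condition | Protocol endpoint 6 | SAP 7.9.1.5 (2) | SAP 7.9.2.4 (2) |
|---|---|---|---|
| Symptoms | required | label only | label only |
| Limb | target limb | none stated | none stated |
| Window | 12 months | 12 months | 60 months |
| Rule for counting | not given | MedDRA code | MedDRA code |

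**2. Does collection restore the symptom condition?** Not for DVT. The scheduled visits in Protocol 10.10 record evidence of thrombus on ultrasound. Protocol 12.3 takes in all target-limb AEs, so a symptom-free DVT is not screened out if the site reports it. The minimum AE data are introduced by "For all reportable AEs, investigators should assess and record at least the following information on the AE CRF". None of the eleven fields that follow is a symptom indicator or a limb field. The event description and narrative are free text.

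**3. Does collection restore the limb condition?** Only in part. Outside the target limb, a subject's DVT is reportable only if it is an SAE. A non-serious DVT in the other limb is not collected, but a serious one is, and the SAP rule would count it.

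**4. Does adjudication restore either?** Not as written. The minimum CEC list in Protocol 13.1 is hypersensitivity, phlebitis, granuloma, EGIT/EHIT and SAEs, all through 12 months. Non-serious DVT is not on it. The CEC Charter, which may say more, is not available here. Whatever the CEC reviews, the SAP reports DVT from the code.

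**5. EGIT and EHIT.** SAP 7.9.1.5 (1) defines these as extension of thrombus into the deep venous system after VenaSeal or thermal ablation, confirmed on ultrasound, with no symptom requirement. It does not say whether such an event also counts as DVT. In the ETA study both arms have a matching category. In the stripping study, a deep extension can be filed as EGIT after VenaSeal but has no such category after stripping.

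**6. Scale.** Planned sizes are about 264 and 108, randomized 1:1, and up to 125 in the VLU Study. The effect of one wrongly included subject is:
- ETA study: 264/2 = 132 per arm; 1/132 = 0.76 points
- Stripping study: 108/2 = 54 per arm; 1/54 = 1.85 points
- VLU Study: 1/125 = 0.80 points

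**The case against.** The SAP still calls the endpoint symptomatic, so the MedDRA sentence can be read as naming the terms used to retrieve it, not as removing the qualifier. Protocol 12.3 names symptomatic DVT as the specific reportable event. A silent clot reaches the count only if a site reports it as an AE and a coder assigns that term. The Charter may cover DVT, and the bias-control list in Protocol 6 can be read as putting target-limb AEs generally before the CEC. The endpoint is secondary and descriptive, and SAP 7.10 lists all AEs anyway.

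Much of this stands. The right claim is that such events can enter the count, not that they will, and no inflation is demonstrated. It does not remove the point, because the SAP gives no step that applies the label: its one stated rule cannot separate the events the label excludes.

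A reader might infer three stronger things that the documents do not support:
- **That PE has the same fault.** Only symptomatic PEs or SAEs are collected, limb ultrasound does not look for PE, and limb is not part of that endpoint.
- **That counting is uneven by arm in general.** Protocol 10.1 puts all subjects on the same assessment schedule, and VenaSeal and ETA each have a thrombus-extension category. Unevenness is possible only in the stripping study, and it depends on coding that the documents do not describe.
- **That the number of extra events can be projected from WAVES**, where 1 of 50 subjects had a thrombus extension on the day 7 scan. Here that finding would be EGIT, which has its own row. WAVES itself reported no DVTs, and the text does not say whether that patient had symptoms.

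**Conclusion.** The point holds for DVT. The SAP's counting rule does not match its own label or protocol endpoint 6. Two kinds of event outside the endpoint can be counted: a symptom-free target-limb DVT found on ultrasound, and a non-target-limb DVT reported as an SAE. For the VLU Study the window also departs from endpoint 6. In the stripping study only, silence on EGIT leaves open whether the two arms' DVT rows contain the same kind of finding.

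The consequence is confined to descriptive safety tables; no primary conclusion depends on it. Its frequency cannot be estimated from the documents, so the size given is the shift per misclassified subject. The conclusion assumes that no unseen document, such as the CEC Charter or detailed CRF specifications, already supplies the symptom and limb conditions.

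**What to change.** Amend SAP 7.9.1.5 (2) and 7.9.2.4 (2) as follows, before DVT tables are produced by arm:
- Use the MedDRA terms, listed explicitly, only to find candidate events.
- Count a DVT only if the AE record or CEC review documents symptoms and target-limb location.
- Report DVT seen only on ultrasound in a separate row.
- State whether EGIT/EHIT is excluded from the DVT row, worded so that a symptomatic DVT that also meets EGIT/EHIT is not lost.
- Align the DVT window with endpoint 6.
- Send candidates to the CEC, which Protocol 13.1 allows to review further AEs when the sponsor asks.

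The cost is SAP wording and review of what should be a small number of existing AE narratives, with no new visits or assessments. The drawback is that symptom status must come from free text. Some events may not be classifiable, and they should be shown as such and not forced into either row.

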4.2.2 Additional Secondary Endpoints in the Randomized Studies

The other secondary objectives of the study are to evaluate the VenaSeal™ system in the treatment of symptomatic venous reflux in the superficial truncal veins. Specific areas of analysis include effectiveness, safety, healthcare utilization, patient experience, and treating physician experience.

Effectiveness endpoints

1. Anatomic closure of the primary target vein at 30 days, and 12, 24, 36, 48 and 60 months
2. Anatomic closure of target vein at 30 days, and 6, 12, 24, 36, 48 and 60 months
3. Technical success of each target vein immediately post-index procedure
4. Reintervention of any target vein (including primary target vein) through 60 months
5. Time to reintervention of any target vein

Safety endpoints

1. Adverse events occurring in the target limb, evaluated from index procedure through 12 months
2. Serious adverse events evaluated through 60 months (through 12 months for VenaSeal vs. Surgical Stripping Study)

Healthcare utilization endpoints

1. Number and type of adjunctive treatments conducted through 12 months post-index procedure
2. Healthcare utilization related to the target limb Venous Reflux Disease through 60 months (through 12 months for VenaSeal vs. Surgical Stripping Study)
3. Procedures, tests, and treatment of AEs related to the treatment modality or index procedure through 60 months (through 12 months for VenaSeal vs. Surgical Stripping Study)

Patient experience endpoints

1. Time to return to normal activities
2. Intra-procedural and post-procedural pain at the index procedure, and 7 days and 30 days
3. Change in venous disease symptoms at 7 and 30 days, and at 6, 12, 24, 36, 48, and 60 months compared to baseline (7 and 30 days, 6 and 12 months only for VenaSeal vs. Surgical Stripping Study)
4. Change in AVVQ score at 30 days, and 6, 12, 24, 36, 48, and 60 months (30 days, 6 and 12 months only for VenaSeal vs. Surgical Stripping Study) compared to baseline
5. Change in EuroQoL Group 5-Dimension Self-Report Questionnaire (EQ-5D-5L) at 30 days, and 6, 12, 24, 36, 48 and 60 months (30 days, 6 and 12 months only for VenaSeal vs. Surgical Stripping Study) compared to baseline
6. Change in the 36-Item Short Form Health Survey (SF-36) reported by the patient at 30 days, and 6 and 12 months compared to baseline

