The probability of experiencing an SAE through 12 months will be summarized by treatment arm in each study. The probability for each treatment arm will be estimated using the Kaplan-Meier method. Day zero is the date of the index procedure. The censoring time is the time to study exit, the later of either the last contact date or the discontinuation date, or the time point for analysis, whichever comes first. The DVT and PE events will be summarized by reporting the number of events of each type and the number of patients in which they occurred, by treatment arm. Additionally, summary statistics will report the proportion of SAEs. Numerator is the number of target limbs (or subjects) with an SAE through 12 months, denominator is the number of target limbs (or subjects).

Determination of Subjects for Analysis

The safety analysis will consist of the ITT population.

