7.9.2.4 Safety secondary endpoints

1. Adverse events (AEs) occurring in the target limb, evaluated from index procedure through 12 months.

Endpoint Definition

- Hypersensitivity to VenaSeal™ adhesive, defined as an allergic reaction to the VenaSeal™ adhesive. The presence of hypersensitivity is confirmed through adjudication. Relatedness to a study procedure and relatedness to the study device are defined.
- Phlebitis, defined as inflammatory reaction of a treated vein. The presence of phlebitis is confirmed through adjudication. Relatedness to a study procedure and relatedness to the study device are defined.
- Granuloma, defined as a grouping of macrophages. The presence of granuloma is confirmed through adjudication. Relatedness to a study procedure and relatedness to the study device are defined.
- Endovenous glue induced thrombosis (EGIT), defined as extensions of a thrombus that extend from the treated vein into the deep venous system. The presence of a glue extension, thrombus extension, or combination glue/thrombus is confirmed through DUS visualization of the extension into the common femoral vein or popliteal vein from the target vein and extension length is specified.

CEC determination of the above events will be used for reporting.

Analysis Methods

Adverse events that are in any of the above enumerated categories will be characterized. Adverse events will be categorized per the specified definitions, and then summarized.

Determination of Subjects for Analysis

The safety analysis will consist of the ITT population.

2. Additional events evaluated through 60 months:

- Symptomatic deep vein thrombosis (DVT) events
- Symptomatic Pulmonary embolism (PE)

- Serious adverse events (SAEs)

Endpoint Definition

CEC determination of serious adverse events will be used for reporting. The MedDRA codes for Deep vein thrombosis and Pulmonary embolism will be used for reporting of DVT and PE adverse events.

Analysis Methods

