The probability of experiencing an SAE through 12 months will be estimated using the Kaplan-Meier method. Day zero is the date of the index procedure. The censoring time is the time to study exit, the later of either the last contact date or the discontinuation date, or the time point for analysis, whichever comes first. The DVT and PE events will be summarized by reporting the number of events of each type and the number of patients in which they occurred. Additionally, summary statistics will report the proportion of SAEs. Numerator is the number of target limbs (or subjects) with an SAE through 12 months, denominator is the number of target limbs (or subjects).

Determination of Subjects for Analysis

The safety analysis will consist of the ITT population.

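### SAEs are a 60-month endpoint in the ETA and VLU studies, but the SAP's SAE Kaplan-Meier estimate and proportion stop at month 12, and SAP 7.9.1.5 also heads PE at 12 months

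*SAP*

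**What the plan says.** **Endpoint horizon.** Protocol 5.2.3, endpoint 7, covers symptomatic PE and SAEs: "Additional events evaluated through 60 months (through 12 months for subjects enrolled in the VenaSeal vs. Surgical Stripping Study". The opening of 5.2.3 applies the secondary endpoints to the VLU study as well. SAP 4.2.2 gives the same horizon for SAEs: "Serious adverse events evaluated through 60 months (through 12 months for VenaSeal vs. Surgical Stripping Study". Symptomatic DVT belongs to a different endpoint, number 6: "Adverse events (AEs) occurring in the target limb, evaluated from index procedure through 12 months".

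**Randomized studies, SAP 7.9.1.5 item 2.** DVT, PE and SAEs share one heading, "Additional events evaluated through 12 months", with no exception for the ETA study. The SAE Kaplan-Meier sentence is "The probability of experiencing an SAE through 12 months will be summarized by treatment arm in each study". The SAE proportion also counts events to month 12, and its "denominator is the number of target limbs (or subjects". DVT and PE get event and patient counts by arm.

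**VLU study, SAP 7.9.2.4 item 2.** The heading is "Additional events evaluated through 60 months". Under it stands "The probability of experiencing an SAE through 12 months will be estimated using the Kaplan-Meier method", with a 12-month proportion as before.

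**General safety.** SAP 7.10 tabulates SAEs to month 60 (12 in the stripping study). It also gives AE counts by arm, severity, type and relatedness, a summary by treatment and preferred term, and listings.

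**Adjudication.** Protocol 13.1 provides for adjudication of SAEs through month 12 as a minimum. SAP 7.9.1.5 and 7.9.2.4 both say that the committee's determination will be used for SAE reporting.

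**The concern.** The SAP's endpoint list and its methods section give different horizons for the same endpoint in the ETA study. In the VLU section the heading and the method differ within one item. A programmer who follows the methods text would produce an SAE probability that covers 12 of the 60 months, leaving 48 of 60 (80%) without an endpoint-level estimate.

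The SAP does separate the studies elsewhere. Time to reintervention (7.9.1.4 item 5) runs to 12 months in the stripping study and to 60 otherwise. The SAP's version history does not list a shorter SAE or PE horizon for the ETA or VLU study. The 12-month text therefore looks like an oversight rather than a decision.

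What is at stake is how the long-term safety of a permanent adhesive is described. From month 12 on, the only committed outputs are counts, percentages and listings, and none of these adjusts for time at risk. Protocol 6.2 itself expects attrition to be higher at 48 and 60 months.

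**Working it through.** **1. Horizons side by side**

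| Source | SAEs | Symptomatic PE | Symptomatic DVT |
|---|---|---|---|
| Protocol 5.2.3, ETA and VLU | 60 months | 60 months | 12 months |
| Protocol 5.2.3, stripping | 12 | 12 | 12 |
| SAP 4.2.2, ETA | 60 | not listed | not listed |
| SAP 7.9.1.5 item 2, ETA and stripping | heading 12; Kaplan-Meier and proportion 12 | 12 | 12 |
| SAP 7.9.2.4 item 2, VLU | heading 60; Kaplan-Meier and proportion 12 | 60 | 60 |
| SAP 7.10, ETA and VLU | tabulated to 60 | within AE summaries to 60 | within AE summaries to 60 |

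Four cells depart from the protocol: SAEs and PE for the ETA study in 7.9.1.5, and the SAE method and DVT in 7.9.2.4. For the stripping study, 12 months is right throughout.

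**2. Size of the gap.** The plan states no 60-month SAE incidence or retention, so there is no figure to reproduce and the rest is conditional.

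Inputs:
- Incidence *I*. The anchor is SAEs in 12 of 242 subjects in the earlier pivotal randomized trial (Protocol 4.1, results including 3-year follow-up): 12/242 = 5.0%. It is used here as a 60-month figure because the extension of that trial reported no SAE from month 36 to 60. The alternative is an assumed 20%.
- Retention *r* at month 60: assumed 90%, 80% or 70%, with linear, non-informative loss.
- Even hazard: λ = −ln(1−*I*)/5 per year.
- Denominator: all randomized subjects (assumed, because SAP 7.10 states none).
- 132 per arm: 264/2, from Protocol 14.1.2.

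Formula. An event at time *t* is seen only if the subject is still followed, so the crude percentage is *I* − ((1−*r*)/5) × *M*, with *M* = (1−e^(−5λ))/λ − 5e^(−5λ).

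- *I* = 4.96%: λ = 0.01017 and *M* = 0.1229. At *r* = 80%, 4.96% − 0.04 × 12.29% = **4.5%**. At 70%, 4.96% − 0.06 × 12.29% = **4.2%**.
- *I* = 20%: λ = 0.04463 and *M* = 0.4814. At 80%, 20% − 0.04 × 48.14% = **18.1%**. At 70%, 20% − 0.06 × 48.14% = **17.1%**.

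False arm difference with equal true risk and 90% versus 70% retention: (0.06 − 0.02) × *M* = 0.04 × *M*.
- At 4.96%: **0.5 points**. Standard error √(2 × 0.0496 × 0.9504/132) = **2.7 points**.
- At 20%: **1.9 points**. Standard error √(2 × 0.2 × 0.8/132) = **4.9 points**.

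If no events occur after month 36, the false differences fall to 0.3 and 1.2 points.

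**3. What the 12-month curve shows.** With even hazard it estimates 1 − (1−*I*)^0.2. That is 1.0% of a true 4.96%, or 4.4% of a true 20%. If half of the cumulative hazard falls in year 1, the 20% case gives 1 − 0.8^0.5 = 10.6%.

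**The case against.** The strongest reply is that the protocol's analysis commitment is already met. Protocol 14.3 promises descriptive safety statistics and SAEs tabulated to month 60, and leaves a Kaplan-Meier plot optional. SAP 7.10 delivers the tabulation. This stands. A reader might infer that SAEs or PEs after month 12 go unreported, and the documents do not support that.

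For PE little turns on the mismatch. The SAP never planned more than counts, and 7.10 summarizes AEs by treatment and preferred term to month 60. The 60-month PE horizon in the ETA study also rests on the protocol alone, since SAP 4.2.2 names only SAEs. This stands too.

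The 12-month cut-off could also be defended because it matches the period of guaranteed adjudication (Protocol 13.1). That is a possible reason, but the SAP does not give it, and it would not reconcile 7.9.1.5 with 4.2.2. Nor does 13.1 show that adjudication ends at month 12: it sets a minimum and allows further events to be adjudicated at the sponsor's request.

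Finally, reporting of follow-up compliance by arm (SAP 7.1.1) and remote visits with AE assessment at 48 and 60 months (Protocol 10.10) limit how far a crude percentage could mislead. This is fair, and it is part of why the point is minor.

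**Conclusion.** The SAP is wrong as written, and the consequence is minor. SAP 7.9.1.5 item 2 gives the wrong horizon for SAEs and PE in the ETA study. The SAE Kaplan-Meier and proportion are also too short in both the ETA and VLU studies. What is lost is the censoring-adjusted SAE estimate from month 12 to 60, not the events themselves. No hypothesis test or claim changes.

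A reader might go further and expect a biased comparison of long-term safety between arms. The documents do not support that. Under the assumptions above, the crude percentage reads low by 0.5 to 0.7 points at an incidence of 5.0%, and by 1.9 to 2.9 points at 20%, for retention of 80% to 70%. The false arm difference stays below sampling error in both cases. The direction of any unequal loss is unknown, and the all-subjects denominator for the 60-month tables is an inference from the denominator defined in 7.9.1.5 and 7.9.2.4. VLU patients may have a higher SAE rate, but that study has no comparison between arms.

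**What to change.** 1. In SAP 7.9.1.5 item 2, state 60 months for SAEs and symptomatic PE in the ETA study and 12 months in the stripping study. Set symptomatic DVT to 12 months in both 7.9.1.5 and 7.9.2.4, to match protocol endpoint 6, or state that the longer VLU horizon is intended.
2. Report the existing SAE Kaplan-Meier estimate at 12 and 60 months with numbers at risk, by arm in the ETA study and overall in the VLU study. Keep the present day zero and censoring rule.
3. Label each SAE after month 12 as committee-adjudicated or investigator-reported, because adjudication is guaranteed only to month 12. A blanket investigator-reported label could be wrong.

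The cost is wording in two SAP sections, one more time point per SAE curve and the status label. No new data or method is needed. The drawback is that the 60-month estimate mixes adjudicated and possibly unadjudicated events, which the label makes visible.
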